### 6.3. Adjustments for Covariates

The study is stratified by country, baseline HbA1c ( $\leq 8.5\%$ ,  $> 8.5\%$  [ $\leq 69$ ,  $> 69$  mmol/mol]), and use of concomitant oral antidiabetic medications (metformin alone, metformin plus an SGLT-2i). Where necessary to be included as a stratification factor, countries with fewer than 10 randomized patients will be pooled into 1 category (pooled country). For HbA1c related analyses, country/pooled country and concomitant oral antidiabetic medication use will be used as stratification factors and baseline HbA1c as a covariate. For other efficacy analyses, country/pooled country, baseline HbA1c ( $\leq 8.5\%$ ,  $> 8.5\%$  [ $\leq 69$ ,  $> 69$  mmol/mol]), and use of

concomitant oral antidiabetic medications (metformin alone, metformin plus an SGLT-2i) will be used as stratification factors and the respective baseline value as a covariate. Stratification factors will be based on the information collected in the clinical database.

#### **6.4. Handling of Dropouts or Missing Data**

For the primary and key secondary efficacy endpoint analyses subject to type 1 error rate control, data for patients with missing values at the 52-week visit will be imputed based on the method described in Section 6.12.1.3. Unless specified otherwise, imputation of missing data will be limited to primary and key secondary efficacy endpoint analyses. Missing other secondary or exploratory efficacy parameter values and missing safety laboratory values will not be explicitly imputed.

#### **6.5. Multicenter Studies**

To investigate potential regional influence on efficacy, country/pooled country will be used as a stratification factor in primary and secondary efficacy analysis.

#### **6.6. Multiple Comparisons/Multiplicity**

The type 1 error rate control strategy for primary and key secondary efficacy objectives is illustrated in Section 6.12.3. As they are intended for different purposes, no multiplicity adjustments will be made for conducting separate analyses relative to the “efficacy” and “treatment-regimen” estimands. In addition, no multiplicity adjustments will be made for evaluating other secondary and exploratory efficacy objectives and safety assessments.

#### **6.7. Patient Disposition**

Reasons for screen failure as reported by investigators will be summarized.

A listing of final study disposition and a listing of randomized treatment assignment (planned treatment) for all randomized patients will be provided. Final study disposition and study treatment disposition for all randomized patients will be summarized by planned study treatment.

#### **6.8. Patient Characteristics**

A listing of patient demographics will be provided for all randomized patients. All demographic and baseline clinical characteristics will be summarized by study treatment for all randomized patients. Baseline demographic and clinical characteristics of special interest including but not limited to: age, gender, race, ethnicity, BMI, weight, country of enrollment, HbA1c, fasting serum glucose, duration of T2DM, baseline antihyperglycemic medication, cardiovascular (CV) history, renal function, history of retinopathy, results of the fundoscopic exam, and history of gallbladder disease.

#### **6.9. Concomitant Therapy**

Prespecified concomitant medications of interest will be summarized by treatment at randomization. Additionally, medications of interest initiated after randomization will be summarized. Concomitant therapies will be mapped using the World Health Organization

(WHO) Drug Dictionary in the clinical trial database and will be further classified using Anatomic-Therapeutic-Chemical (ATC) codes for reporting purposes.

Concomitant medications of interest include the following groups of medication:

- baseline antihyperglycemic therapy
  - prior glucagon-like peptide-1 receptor agonist (GLP-1 RA) use by type
  - metformin
  - sodium/glucose cotransporter-2 -inhibitors, by type
- baseline antihypertensive therapy, by type
- baseline lipid lowering therapy, by type
- changes to baseline medication in Study Period II:
  - antihypertensive therapy
  - lipid lowering therapy
- changes to baseline medication during Study Periods II and III:
  - antihyperglycemic therapy
- rescue therapy due to severe persistent hyperglycemia
- utilization of:
  - antidiarrheal medication
  - antiemetic medication

## 6.10. Treatment Exposure and Compliance

A listing of patients randomized but not receiving study treatment will be provided, if applicable. The listing will include patient identification, randomized treatment arm, and the reason for not receiving study treatment.

A listing of randomized patients who inadvertently received incorrect study treatment anytime during the study will be provided, if applicable. The listing will include patient identification, randomized treatment arm, and information related to the treatment incorrectly received: incorrectly received study treatment, start and stop dates during which the incorrect treatment was received.

Summary of duration of follow-up (defined as time in days from date of randomization to date of the safety follow-up visit) and duration on study treatment (defined as time in days from date of first dose of study treatment to date of last dose of study treatment plus 7 days) will be provided by therapy.

### 6.10.1. Exposure and Compliance to Tirzepatide

The number of patients prematurely discontinuing study treatment prior to the 52-week visit will be provided by study treatment. Reasons for prematurely discontinuing study treatment prior to

the 52-week visit will also be provided by study treatment. A time-to-event analysis of premature study treatment discontinuation will be conducted.

The proportion of patients with missing dosing information, receiving no LY dose, receiving 2.5 mg, 5 mg, 7.5 mg, 10 mg, 12.5 mg, or 15 mg will be presented by randomized treatment and week from first dose.

A listing and summary of patients continuing on a reduced maintenance dose of tirzepatide compared to the randomized dose may be provided.

Compliance will be defined as taking at least 75% of the scheduled tirzepatide doses. Compliance will be calculated by taking the number of doses administered (regardless of the actual dose administered) divided by the total number of doses expected to be administered  $\times 100$ . Treatment compliance will be summarized descriptively over the entire study period by treatment using the mITT population.

### **6.10.2. Exposure and Compliance to Insulin Degludec Treat-to-Target Algorithm**

Summary information on total daily dose of insulin degludec will be reported by visit. Information related to compliance to treat-to-target therapy including reasons for non-compliance will be summarized.

Compliance will be defined as taking at least 75% of the scheduled insulin doses. Compliance will be calculated by taking the number of doses administered (regardless of the actual dose administered) divided by the total number of doses expected to be administered  $\times 100$ . Treatment compliance will be summarized descriptively over the entire study period by treatment using the mITT population

Additionally, summaries will be produced for the percent of patients to reach fasting serum glucose goals of  $<90$  mg/dL (5 mmol/L) and  $<126$  mg/dL (7 mmol/L) over time at weeks 16, 24, 40, and 52.

## **6.11. Important Protocol Deviations**

Important protocol deviations are identified in the Trial Issues Management Plan (TIMP). A listing and a summary of important protocol deviations by treatment will be provided.

## **6.12. Efficacy Analyses**

For the Food and Drug Administration (FDA) and potentially for other regulatory agencies, all efficacy assessments will be guided by the “treatment-regimen” estimand conducted using the FAS. Assessment of the primary and secondary efficacy objectives subject to type 1 error rate control (key secondary) will be conducted with multiple imputation of missing data (see Section 6.12.1.3) at 52 weeks. Assessment of other efficacy objectives will be conducted without imputation of missing data. For publications and other purposes, the assessment of efficacy objectives will be guided by the “efficacy” estimand using the EAS without imputation of missing data.

### **6.12.1. Primary Efficacy Analysis**

The primary efficacy measure will be change in HbA1c from baseline (postbaseline – baseline). Both HbA1c values as well as change from baseline in HbA1c will be summarized by treatment and nominal visit (week). When applicable, HbA1c data from a local lab will be used when central lab data are not available. If scheduled HbA1c data at the primary endpoint visit are not available, unscheduled HbA1c data collected for the primary endpoint visit will be included in the analysis.

#### **6.12.1.1. The Analysis Relative to the Efficacy Estimand**

The analysis will be conducted utilizing HbA1c data in the EAS from baseline through the 52-week visit with the aid of a mixed model for repeated measures (MMRM). Restricted maximum likelihood (REML) will be used to obtain model parameter estimates and the Kenward-Roger option will be used to estimate the denominator degrees of freedom. The response variable of the MMRM model will be the primary measure and model terms will include treatment, visit, treatment-by-visit interaction, country/pooled country, and baseline concomitant oral antihyperglycemic medication use (metformin alone versus metformin plus an SGLT-2i) as fixed effects and baseline HbA1c as a covariate. An unstructured covariance structure will be used to model the within-patient errors. If this model fails to converge, the following covariance structures will be tested in order:

- heterogeneous Toeplitz
- heterogeneous first order autoregressive
- heterogeneous compound symmetry
- Toeplitz
- first order autoregressive
- compound symmetry

The first covariance structure that converges will be used. The resulting least squares mean (LSM) estimates of mean change from baseline in HbA1c will be plotted by visit and by study treatment.

With the aid of the MMRM analysis, 2-sided 97.5% confidence intervals (CI) for mean change in HbA1c from baseline to the 52-week visit for (10 mg tirzepatide – insulin degludec) as well as for (15 mg tirzepatide – insulin degludec) will be derived. If the upper limit of the CI is  $\leq 0.3\%$ , then the respective dose of tirzepatide (10 mg and/or 15 mg) will be declared noninferior to insulin degludec relative to change in HbA1c from baseline.

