For all other purposes, the primary efficacy analysis will be guided by the “efficacy” estimand defined in Section 10.3.1. This assessment will be conducted using EAS. The primary analysis model for HbA1c measurements over time will be an MMRM. The response variable of MMRM will be change in HbA1c from baseline values obtained at each scheduled postbaseline visit. The independent variables of the MMRM model are treatment, visit, and treatment-by-visit interaction, country, baseline concomitant oral antidiabetic treatment (metformin alone, metformin plus an SGLT-2 inhibitor) as fixed effects, and baseline HbA1c as a covariate. Two-sided 97.5% CIs will be constructed for the difference in mean change in HbA1c from baseline to the 52-week visit between LY3298176 10 mg and insulin degludec, as well as between LY3298176 15 mg and insulin degludec. If the upper limit of the CI is below 0.3%, the LY3298176 dose will be declared noninferior to insulin degludec.

Since they are intended for different purposes, each of the 2 primary efficacy assessments will be conducted at a family-wise type 1 error rate of 0.05. Additional details, including analysis methods for key secondary endpoints and a strategy for controlling the overall family-wise type 1 error rate at an alpha of 0.05 for primary and key secondary endpoint evaluation will be provided in the SAP.

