### **6.12.2.2. Mean Change in Body Weight from Baseline at the 52 Week Visit**

The analysis for change in body weight from baseline (postbaseline – baseline) will be conducted in a manner similar to the primary analysis in Section 6.12.1. Baseline HbA1c concentration ( $\leq 8.5\%$ ,  $> 8.5\%$  [ $\leq 69$ ,  $> 69$  mmol/mol]) will be used as a fixed factor in place of baseline HbA1c as a covariate and baseline body weight will be used as an additional covariate in the statistical model. Least squares mean estimates of mean change in body weight from baseline will be plotted by nominal visit and by study treatment. For multiple imputation of missing values, if the imputed value of weight change from baseline is  $< -50$  kg or  $> 50$  kg, then that value will be set to  $-50$  kg or  $50$  kg, respectively, to avoid unrealistic imputed values.

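### The efficacy-estimand MMRM fits one baseline-HbA1c slope to all visits from Week 4 to Week 52; if the true slope steepens over time, the Week 52 interval is wider than it needs to be

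*SAP*

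**What the plan says.** SAP 6.12.1.1 states that "model terms will include treatment, visit, treatment-by-visit interaction, country/pooled country, and baseline concomitant oral antihyperglycemic medication use" enter "as fixed effects and baseline HbA1c as a covariate". Protocol 10.3.3.1 has the same structure: "treatment, visit, and treatment-by-visit interaction, country, baseline concomitant oral antidiabetic treatment" are listed "as fixed effects, and baseline HbA1c as a covariate". Neither lists a baseline-by-visit term, and the covariate rules in SAP 6.3 do not supply one.

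The response is "change in HbA1c from baseline values obtained at each scheduled postbaseline visit". The Schedule of Activities puts these HbA1c measurements at Weeks 4, 8, 12, 16, 20, 24, 40 and 52, which is eight visits. The SAP adds: "An unstructured covariance structure will be used to model the within-patient errors". The noninferiority decision rests on "2-sided 97.5% confidence intervals (CI) for mean change in HbA1c from baseline to the 52-week visit" for each of 10 mg and 15 mg against degludec.

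Two related models matter here. For body weight, SAP 6.12.2.2 says that "baseline body weight will be used as an additional covariate in the statistical model", again with no visit interaction. For the HbA1c <7% endpoint under the efficacy estimand, SAP 6.12.2.3 fills in missing HbA1c from an MMRM with the same terms before dichotomising. The other primary analysis (SAP 6.12.1.2) is an ANCOVA on Week 52 alone, so its baseline slope is already specific to Week 52.

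**The concern.** A constant slope is a restrictive assumption in this design. At Week 4 every tirzepatide arm has had only the starting dose. Protocol 7.7.1 treats escalation as lasting 24 weeks, and Protocol 5.1 expects most degludec titration in the first 16 weeks. Change in HbA1c may therefore depend on baseline less at Week 4 than at Week 52.

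If so, an MMRM with one slope and unstructured covariance estimates a weighted compromise. The weights favour the early visits when those have the smaller residual variance. The compromise slope is then too shallow for Week 52, and the unexplained part of the baseline effect goes into the Week 52 residual variance. At stake is the width of the Week 52 interval for the efficacy estimand, and the quality of the values imputed for the <7% endpoint.

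**Working it through.** **1. The plan's own figure.** Inputs (SAP 5.2): difference 0.35, superiority margin 0.05 (net 0.30), SD 1.1, two-sided 0.025 per dose, 28% rescue or discontinuation, 355 per arm.
- Per arm at 80% power per dose: 2 x (1.1/0.30)^2 x (2.241 + 0.842)^2 = 256. Then 256/0.72 = 356, and 4 x 356 = 1424, against 1420 stated.
- With 355 x 0.72 = 255.6 evaluable per arm, power is 80.0% per dose and 91.3% for at least one of two doses (correlation 0.5). This reproduces the claim of at least 90%.
- The calculation is an unadjusted t-test. Its 97.5% half-width is 2.241 x 1.1 x sqrt(2/255.6) = 0.218.

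**2. Formula for the excess width.** The documents give no baseline SD, visit-specific slopes or visit covariance, so these are assumptions. Let b be the vector of true slopes, S the residual covariance, 1 a vector of ones and SDx the baseline SD.
- Large-sample common slope: bc = (1'S^-1 b)/(1'S^-1 1).
- Week 52 residual variance with visit-specific slopes: v = 1.1^2 - b52^2 x SDx^2.
- Week 52 residual variance with a common slope: v + (b52 - bc)^2 x SDx^2.
- Interval ratio: the square root of the second over the first.

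**3. Numbers put in (SDx 0.8).**
- Equal slopes: bc = b52, ratio 1.000.
- -0.40 to -0.55, bc about -0.40: v = 1.210 - 0.194 = 1.016; added 0.15^2 x 0.64 = 0.014; ratio 1.007.
- -0.4 to -0.7, bc -0.35: v = 1.210 - 0.314 = 0.896; added 0.35^2 x 0.64 = 0.078; ratio 1.043.
- -0.2 to -0.7, bc -0.13: v = 0.896; added 0.57^2 x 0.64 = 0.208; ratio 1.110.

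**4. Sensitivity to the covariance.** The grid was Week 4 slope -0.15 to -0.40, Week 52 slope -0.55 to -0.70 and SDx 0.8 to 1.0. Correlation decayed with visit distance. The Week 4 residual SD was half that of Week 52, and slopes and SDs changed linearly to Week 24.
- Adjacent-visit correlation 0.7: 0.4% to 11% wider.
- Correlation 0.8: 0.5% to 14%.
- Correlation 0.9: 0.8% to 22%.
- Equal residual SD at all visits, correlation 0.7: 0.1% to 4%.

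**5. Simulation of both models.** Eight visits, 355 per arm, about 28% dropout, randomisation stratified at 8.5%, baseline SD about 0.8, unstructured covariance fitted by maximum likelihood.

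| Slope, Week 4 to Week 52 | Half-width, common slope | Half-width, by visit | Excess |
|---|---|---|---|
| -0.5 to -0.5 | 0.190 | 0.190 | 0% |
| -0.2 to -0.5 | 0.197 | 0.190 | 3.5% |
| -0.4 to -0.7 | 0.177 | 0.170 | 4.0% |
| -0.2 to -0.7 | 0.188 | 0.171 | 10.4% |
| -0.1 to -0.8 (extreme) | 0.191 | 0.158 | 21% |

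**6. Lost information or overstated SE?** In the -0.2 to -0.7 case (400 runs), the reported SE was 0.0840 with a common slope and 0.0761 by visit, a ratio of 1.104. The empirical SEs were 0.0777 and 0.0751, a ratio of 1.035. So about 3.5% of the 10.4% is real loss, and the rest is a reported SE that is too large. A separate simulation (3000 trials, 256 per arm, SDx 0.9) agrees. Its reported SEs were 0.0872 and 0.0839 (3.9% wider), while the empirical variance ratio under stratification was 1.026, or sqrt(1.026) = 1.013 on the SE scale.

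**7. Power in the same case, at net 0.30.** Common slope: 0.30/0.0840 - 2.241 = 1.33, giving 90.8%. By visit: 0.30/0.0761 - 2.241 = 1.70, giving 95.6%. Both exceed the planned 80.0% per dose.

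Limits: the simulations in step 5 used ML rather than REML with Kenward-Roger, omitted country and oral medication, and ran 120 to 400 trials per scenario.

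**The case against.** The strongest reply is that the model is prespecified and valid, and that the gain from changing it is unknown. Much of this stands. A reader might go further than the documents allow in five ways:

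- **That the interval is wider as a matter of fact.** The documents describe escalation and titration but never say how change in HbA1c depends on baseline at any visit. With equal slopes the cost is nil.
- **That the trial is underpowered.** The sample size takes no credit for baseline adjustment, so what is forgone is surplus precision.
- **That every primary result is affected.** The FDA primary is the Week 52 ANCOVA, which does not have this restriction.
- **That the treatment estimate is biased.** In the step 5 setting it was not: -0.345 with a common slope and -0.344 by visit, against a true -0.35, with coverage of about 98% in both. Bias appears only if dropout depends on baseline differently by arm. In a deliberately strong case, the odds of degludec dropout alone rose 2.7-fold per 1% of baseline HbA1c. With steepening slopes, this moved the common-slope estimate to between about -0.36 and -0.40, while the by-visit estimate stayed within about 0.01 of -0.35. Nothing in the documents establishes such a pattern, so this is a further reason for the term and not a finding of bias.
- **That every other MMRM in the SAP loses as much.** Only HbA1c was calculated. Body weight has the same model structure, but no size can be given for it.

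It is also fair to say that the change has a procedural cost, because the Protocol itself names the model terms.

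**Conclusion.** The point holds as a conditional loss of efficiency in one of the two primary analyses. The restriction to one slope is certain from the text; its cost depends on slopes that the documents do not give. Under moderate assumed slopes and baseline SD 0.8 to 1.0, the reported Week 52 interval is about 1% to 11% wider than needed. The upper end rises if visits are more strongly correlated than assumed, and the excess is zero if slopes are equal. Most of the excess is an overstated standard error, because stratification on baseline HbA1c already balances much of what the model fails to adjust for. The analysis is then conservative, provided that dropout does not depend on baseline differently by arm. The change is worth making because it costs so little, not because the current analysis is unsound.

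**What to change.** - **SAP 6.12.1.1:** add baseline HbA1c-by-visit to the MMRM.
- **SAP 6.12.2.3:** add the same term to the MMRM that imputes missing HbA1c for the <7% endpoint.
- **SAP 6.12.2.2:** add baseline weight-by-visit to the body-weight MMRM.

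The cost for HbA1c is seven fixed-effect parameters (eight visits less one) with about 1420 patients. For weight it is eight, since the schedule has nine post-baseline treatment-period weights, including Week 32. The current model is nested in the new one, and with equal slopes the simulated SE was 0.0848 under both, so the effect on precision is negligible.

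Protocol 10.3.1 and SAP 6.2 require a change to a protocol-described method to be recorded with its justification, and an amendment if a principal feature changes. The sponsor should decide which applies and record the change in the SAP before results are known, which matters more in an open-label trial.

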#### **6.12.1.2. The Analysis Relative to the Treatment Regimen Estimand**

The analysis will be conducted utilizing HbA1c data in the FAS at baseline and at the 52-week visit with the aid of an ANCOVA. The response variable will be the primary measure and model terms will include treatment, country/pooled country, and baseline concomitant oral antihyperglycemic medication use (metformin alone versus metformin plus an SGLT-2i) as fixed

effects and baseline HbA1c as a covariate. The ANCOVA analysis will be conducted with multiple imputation of missing primary measures (see Section 6.12.1.3 for details) and statistical inference over multiple imputation of missing data guided by Rubin (1987).

With the aid of the ANCOVA analysis 2-sided 97.5% CI for mean change in HbA1c from baseline to the 52-week visit for (10 mg tirzepatide – insulin degludec) as well as for (15 mg tirzepatide – insulin degludec) will be derived. If the upper limits of the CI are  $\leq 0.3\%$ , then the respective dose of tirzepatide (10 mg and/or 15 mg) will be declared noninferior to insulin degludec relative to change in HbA1c from baseline.

### **6.12.1.3. Methods for Multiple Imputations**

For efficacy analyses relative to the “treatment-regimen” estimand, missing HbA1c data at the 52-week visit will be imputed based on “retrieved dropouts,” defined as patients who had their HbA1c value measured at the 52-week visit in the same treatment arm who prematurely discontinued study drug. If the imputed value of HbA1c change from baseline is  $< -6.0\%$  or  $> 6.0\%$ , then that value will be set to  $-6.0\%$  or  $6.0\%$ , respectively, to avoid unrealistic imputed values.

### **6.12.1.4. Additional Analyses of the Primary Outcome**

Upon successfully establishing noninferiority of tirzepatide compared to insulin degludec, superiority of tirzepatide compared to insulin degludec relative to change in HbA1c from baseline will be evaluated (see Section 6.12.3).

